12.1.5 End of Study Definition

A participant is considered to have completed the study if he or she has completed all phases of the study including screening, enrollment,

PI: [name]

procedure and the 10 minute skin assessment after pad removal.

The end of the study is defined as completion of the last visit shown in the Schedule of Activities.

12.2 Analytics

All analyses will be performed on an intention to treat basis. We calculated the sample size on the basis of the 3 prior randomized studies that compared RBW and BTE shocks for DCCV of AF. In these studies, the mean overall shock success was 90-97% and the first shock success varied from 54%-90% albeit the first shock was delivered at a lower energy than maximum output. We therefore estimate that the mean first shock success rate will be 93%. A clinically meaningful difference in first full output shock efficacy is 5%. A total study sample size of 544 patients (272 in each group) is needed to provide a power of 80% to reject the null hypothesis (a difference in efficacy of < 5%).

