Efficacy Evaluations:	
 1. Proportion of patients in NSR by ECG or monitor 1 minute after the first DCCV shock. 2. Proportion of patients in NSR by ECG or monitor 1 minute after the first or second DCCV shock. 3. Proportion of patients in NSR by ECG or monitor 1 minute after a third or fourth crossover treatment assignment shock after failing first and second shock on original treatment assignment.
Safety Evaluations:	
 1. Number of patients with skin redness, pain or discomfort under the shock electrodes (excluding those with cross-over) 2. Number of patients with arrhythmic events (asystole, atrioventricular block, transient bradycardia or ventricular arrhythmia) within 10 minutes of the last DCCV shock 3. Frequency of pacemaker or ICD dysfunction after shock among patients with prior pacemaker or defibrillator implant
Statistical and Analytical Plan:	
Based on the best available literature we expect the first shock DCCV success rate to be 93% in our population. A total sample size of 538 subjects (269 in each group) will be needed to provide 80% power to reject the null hypothesis (a difference of efficacy < 5%). The analysis will be performed on the intention-to-treat population. The proportions will be compared using both risk difference and risk ratio with corresponding 95% CI. Effects of treatment will be estimated by modified

A Pragmatic Randomized Clinical Trial Comparing Rectilinear Biphasic Waveform and Biphasic Truncated Exponential Waveform Shocks for Cardioversion of Atrial Fibrillation (Zoll vs Lifepak-RCT) |

PI: [name]

	Poisson regression using generalized estimating equations. Outcomes will be compared across pre-specified subgroups and testing will be performed for interactions (sex, body mass index, first or > 1 AF episode, AF type, DCCV location).
Data and Safety Monitoring Plan:	The study PI will be responsible for study safety. One interval analysis will be performed after 50% trial enrollment. No DSMB will be assembled.

TABLE OF CONTENTS

STUDY TITLE.....	Error! Bookmark not defined.
SUMMARY OF CHANGES	i
ABSTRACT	ii
ABBREVIATIONS AND DEFINITIONS.....	iii
PROTOCOL SYNOPSIS	iv
TABLE OF CONTENTS	viii
SCHEMA EXAMPLES.....	Error! Bookmark not defined.
1. BACKGROUND.....	2
1.1 Study Disease(s) or Condition(s)	2
1.2 Product(s) / Agent(s)	2
1.3 Rationale	3
1.4 Relevant Literature and Data	3
1.5 Correlative Studies Background	5
1.6 Compliance Statement.....	5

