1.4 Relevant Literature and Data

In 1959 Lown developed a direct current waveform to improve efficacy and reduce adverse events associated with defibrillation performed with alternating current. The monophasic waveform he developed was in use until the 1980s when biphasic waveforms were shown to further improve defibrillation success. Several biphasic waveforms have been developed including the BTE and RBW waveforms. These waveforms have been incorporated into competing FDA approved devices manufactured by Zoll, Phillips, and Physiocontrol/Medtronic.

- The first comparative study of biphasic DCCV shock waveforms was published in 2003³. Investigators randomized 101 patients with AF to DCCV using escalating RBW shocks from a Zoll M series defibrillator (50, 100, 200, 200J) or escalating BTE shocks from a Physiocontrol Lifepak-12 defibrillator (50, 100, 200, 200J). If the fourth shock at 200J failed in either arm a single 360J shock was delivered from the BTE device. Patches were placed in an antero-posterior location. The overall efficacy was 97.9% in the BTE group and 100% in the RBW group (p=0.29). The study was underpowered to detect a clinically significant difference between groups. Enrollment would have allowed the study to detect an efficacy difference of 20% or more.
- The second observational study was published in 2004⁴. Patients with AF underwent DCCV with a series of escalating RBW shocks from a Zoll series M

A Pragmatic Randomized Clinical Trial Comparing Rectilinear Biphasic Waveform and Biphasic Truncated Exponential Waveform Shocks for Cardioversion of Atrial Fibrillation (Zoll vs Lifepak-RCT) |

PI: [name]

defibrillator (50,100,150, 200J) or a BTE shock (50,100,150, 300, 360J) from a Medtronic Physiocontrol Lifepak 12 defibrillator. If DCCV was unsuccessful at the maximum deliverable energy patients were crossed over to the other device. Patches were placed in an antero-posterior location. 145 patients were enrolled but treatment allocation was not randomized because of patient refusal or physician refusal to participate in the study. The success rate was 97% in both groups ($p=1.0$). 2/71 patients in the RBW group failed maximum energy shock (200J) and crossed over to the 360J RBW shock and were successfully converted. 2/71 patients in the BTE group failed maximum energy shock (360J) and crossed over to the RBW group. Both also failed the RBW shock.

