- The third comparative study of the RBW and BTE waveforms was published in 2005⁵. The investigators randomized 188 subjects with AF in a 1:1 fashion to receive escalating low energy RBW shocks (50, 75, 100, 120, 150, 200 J) or BTE shocks (50, 70, 100, 125, 150, 200, 300, 360 J). The shock strength was escalated until success or maximum energy was delivered. If maximum energy shock failed, the patient crossed over to the opposite waveform. 47 patients were excluded leaving a total of 141 patients (71 in RBW and 70 with BTE shocks). The authors found a maximum energy success rate of 93% in patients receiving a RBW shock and 97% in patients receiving a BTE shock ($p=0.44$). Unfortunately, the small study sample size would have allowed the authors to detect a minimum difference in success rate of 14% or more, while a clinically relevant efficacy difference of 5% or more was impossible to detect.
- The fourth comparative study of commercially available biphasic waveforms was published in 2013⁶. The investigators randomized 199 patients to receive DCCV using either a RBW from a Zoll series R defibrillator or BTE from a Phillips Heartstart XL defibrillator using 50, 100, 150, 200, 200 J. The shock strength was escalated until success or maximum energy was delivered. 95% of patients in the RBW and 90.9% of patients in the BTE arms successfully converted to NSR ($P=0.838$). Unfortunately, the small study sample size allowed the study to detect differences in efficacy of 20% or more and they did not deliver maximal energy (360J) shocks using the BTE waveform, limiting the clinical applicability of the findings.
- Since the 4 comparative studies were published, a randomized controlled study in 2021 showed anterolateral patch placement improved DCCV success rate compared to anteroposterior placement⁹. Further, a DCCV protocol using fixed maximum energy shocks was found to be more effective than escalating low-energy shocks⁷. No adequately powered studies have compared a first maximum shock efficacy of RBW (200J) to BTE (360J) waveforms incorporating these recommendations and an anterolateral patch location.

Correlative Studies Background

1.4.1 NA

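### The 93% first-shock planning rate is an extrapolation that no quoted figure supports, and the stated 80% power holds at 93% v 98%, not at a mean of 93%

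*Combined protocol and SAP*

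**What the plan says.** Section 12.2 (Analytics) bases the sample size on the three earlier randomised comparisons of the two waveforms: "In these studies, the mean overall shock success was 90-97% and the first shock success varied from 54%-90" per cent. The sentence goes on, "albeit the first shock was delivered at a lower energy than maximum output". The next one concludes: "We therefore estimate that the mean first shock success rate will be 93" per cent. The target effect follows: "A clinically meaningful difference in first full output shock efficacy is 5" per cent. Section 12.2 then gives 544 patients (272 per arm) for 80% power. The synopsis gives 538 (269 per arm) for the same power and attributes the rate to the literature: "Based on the best available literature we expect the first shock DCCV success rate to be 93% in our population".

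Section 1.4 summarises the same three randomised studies:

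- 2003: "The overall efficacy was 97.9% in the BTE group and 100% in the RBW group".
- 2005: "The authors found a maximum energy success rate of 93% in patients receiving a RBW shock and 97% in patients receiving a BTE shock".
- 2013: "95% of patients in the RBW and 90.9% of patients in the BTE arms successfully converted to NSR".

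Section 1 says that all the earlier studies began at low energy and escalated over several shocks. The primary endpoint in section 12.1.1 is sinus rhythm one minute after a single full-output shock.

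**The concern.** The planning rate for a single shock lies above every first-shock rate that the protocol quotes and inside the range it gives for overall success, which is a different quantity. That overall range also disagrees with the protocol's own literature summary. The protocol does not show how it reached 93%.

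The input matters because the variance of a proportion rises quickly as success falls away from 100%. A 5-point difference is much easier to detect near the ceiling than a few points lower. If the two devices convert fewer patients on the first shock than the calculation assumes, a non-significant result would be read against a claimed 80% power that the trial did not have. The protocol describes the trial as adequately powered, which makes that reading more likely.

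**Working it through.** **1. The literature figures.** Arm rates in section 1.4 for the three randomised studies:

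| Study | RBW | BTE | Simple mean | Longest shock sequence |
|---|---|---|---|---|
| 2003 | 100% | 97.9% | 98.95% | 5 (four, then one at 360 J) |
| 2005 | 93% | 97% | 95.0% | 6 (RBW) or 8 (BTE) |
| 2013 | 95% | 90.9% | 92.95% | 5 |

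By arm the range is 90.9% to 100%; by study mean it is about 93% to 99%. Neither is 90% to 97%, and both arms of the 2003 study lie above that upper limit. All six rates are cumulative over an escalating sequence. The only first-shock rates quoted are 54% to 90%, all below maximum output. The abstract and synopsis also give a general success rate of 90% to 95%, but do not tie it to the first shock.

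**2. Reproducing the sample size.** Inputs: 5-point difference, 80% power and 1:1 allocation (all stated); two-sided alpha 0.05 (assumed; the plan gives no alpha, but its hypothesis is non-directional and its intervals are 95%). With p̄ the average of the two arm rates and d their difference, define

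A = √[2p̄(1−p̄)], B = √[p₁(1−p₁) + p₂(1−p₂)], n per arm = (1.960·A + 0.842·B)² / d².

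At 93% v 98%: p̄ = 0.955, A = 0.2932, B = 0.2910, so n = (0.5747 + 0.2449)² / 0.0025 = 268.7, rounded up to 269 per arm, or 538. That is the synopsis figure exactly, and it is within 3% of 544. Other readings do not fit: 88 v 93 needs 539 per arm and 90.5 v 95.5 needs 408. So the calculation takes 93% as the *lower* arm, and the average rate it implies is (93 + 98)/2 = 95.5%.

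**3. Power at 272 per arm for a 5-point difference.** Power = Φ[(d√n − 1.960·A)/B], with d√n = 0.05 × √272 = 0.8246.

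| Arm rates | Average | A | B | z | Power |
|---|---|---|---|---|---|
| 94 v 99 | 96.5% | 0.2599 | 0.2575 | 1.224 | 89.0% |
| 93 v 98 | 95.5% | 0.2932 | 0.2910 | 0.859 | 80.5% |
| 90.5 v 95.5 | 93.0% | 0.3608 | 0.3591 | 0.327 | 62.8% |
| 90 v 95 | 92.5% | 0.3725 | 0.3708 | 0.255 | 60.1% |
| 88 v 93 | 90.5% | 0.4147 | 0.4132 | 0.029 | 51.1% |

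The third row is the literal reading of a mean of 93%. The fourth puts the lower arm at the top of the quoted first-shock range. The 88% in the last row is an assumption; no document gives it as a first-shock rate.

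**The case against.** The strongest defence is that the plan discloses the extrapolation. It says that the 54% to 90% came from shocks below maximum output, so those rates are not like for like with a full-output first shock. Section 1.4 also gives reasons to expect better results: fixed maximum energy did better than escalation, and anterolateral pads did better than anteroposterior. This stands as far as direction goes, and full-output first-shock success could equal or exceed 93%. It does not show how large the gain is, and the plan offers no sensitivity range.

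Three stronger readings are tempting, and the documents do not support them:

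- A reader might infer that the trial is powered on the wrong endpoint. It is not. Section 12.2 ties the 5-point difference to the first full-output shock, which is the endpoint in section 12.1.1. At most the base rate is borrowed from cumulative success, and even that is inference, because no derivation is shown.
- A reader might infer that the misstated range distorts the sample size. It does not enter the formula, and restoring the 2003 results raises the mean of the six arm rates to 95.6%.
- A reader might infer that no cited study reports a full-output first-shock rate. That cannot be checked here: the protocol cites a trial of fixed maximum-energy shocks without giving its rates. Only the protocol's own silence can be stated.

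It is also fair to say that the planned risk difference and risk ratio with 95% intervals limit over-reading of a null result. They do not correct the power claim.

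**Conclusion.** The point holds as a gap in justification together with an overstated power claim; the sample-size arithmetic itself reproduces. The 93% is unsupported by any first-shock figure quoted in the protocol, and the overall range in section 12.2 contradicts section 1.4. The 80% is conditional on arm rates of 93% and 98%. At the mean of 93% that the plan states, power is 63%, about 18 points lower; at 90 v 95 it is 60%. It could also be higher: 89% at 94 v 99.

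These figures assume a two-sided 0.05 test of no difference without continuity correction, which is the form that reproduces the synopsis figure, and 272 evaluable patients per arm. Two related matters are separate: the plan does not say which side of 93% the 5-point difference falls, and 538 and 544 need reconciling.

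**What to change.** In section 12.2:

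- Replace 90% to 97% with 90.9% to 100% by arm, labelled as cumulative success after escalating shocks.
- State that the protocol quotes no first-shock rate at full output and that 93% is an extrapolation, with the reasoning behind it.

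In section 12.2 and the synopsis:

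- Replace the unconditional 80% with power conditional on both arm rates at 272 per arm, naming the alpha and sidedness. For example: 89% at 94 v 99, 80% at 93 v 98, 63% at 90.5 v 95.5, 60% at 90 v 95, and 51% at 88 v 93. Mark rates below 90% as assumptions.

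The misstated range appears only in section 12.2, so the synopsis needs the power change alone. The sample size, endpoints and procedures stay as they are. The cost is wording in two places and a less favourable stated power.

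### The 80% power for a 5-point difference holds only for 93% v 98% tested against zero; the plan states neither, words its null as a difference below 5%, and has about 63% power if 93% is the mean of the two arms

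*Combined protocol and SAP*

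**What the plan says.** Section 12.2 summarises the earlier randomised studies: "the mean overall shock success was 90-97% and the first shock success varied from 54%-90" per cent, the latter at lower than maximum energy. It then says "We therefore estimate that the mean first shock success rate will be 93" per cent, names 5% as the clinically meaningful difference, and continues: "A total study sample size of 544 patients (272 in each group) is needed to provide a power of 80" per cent. What the trial is meant to have this power for is worded as follows: "to reject the null hypothesis (a difference in efficacy of < 5" per cent).

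The Statistical and Analytical Plan row of the Protocol Synopsis makes the same argument with different numbers: "we expect the first shock DCCV success rate to be 93% in our population", and "A total sample size of 538 subjects (269 in each group) will be needed to provide 80% power". There too the purpose of the calculation is worded against a threshold: "reject the null hypothesis (a difference of efficacy < 5" per cent). On analysis it says: "The proportions will be compared using both risk difference and risk ratio with corresponding 95% CI".

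Section 5.1.1 hypothesises that the two waveforms differ in first-shock efficacy by more than 5%, without a direction. Section 8.1.2 (Projected Participants) expects 560 enrolled to give 544 evaluable. Sections 1.3 and 1.4 justify the trial on the ground that earlier studies were too small and this one is large enough.

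No section gives the assumed rate in each arm, the alpha, the number of sides or the test.

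**The concern.** A power statement for two proportions needs two rates. The plan gives one, and does not say whether 93% is the lower arm, the higher arm or the average of both. Near 100% this matters: the variance falls quickly as the rates rise, so the same 5-point gap needs far fewer patients at 93% v 98% than at 90.5% v 95.5%.

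The null is a second problem. If the hypothesis to be rejected is that the difference is below 5 points, a true difference of 5 points lies at its edge, and no sample size gives 80% power to reject it.

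At stake is the trial's main justification. If power for 5 points is nearer 63%, a true difference of that size would be missed about 37% of the time (100 − 62.8 = 37.2). A reader who takes the stated null literally would also expect a positive result to show that the difference exceeds 5 points, which this design cannot be relied on to do when the true difference is 5.

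**Working it through.** **Inputs from the documents.** 93% first-shock success, 5-point difference, 80% power, and 272 per arm (section 12.2) or 269 per arm (synopsis); 1:1 allocation (section 5.3).

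**Assumptions not in the documents.** Two-sided alpha 0.05, consistent with the planned 95% CI; pooled-variance z-test of zero difference; no continuity correction.

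**Formulas.** With p̄ = (p1 + p2)/2, A = √[2p̄(1 − p̄)] and B = √[p1(1 − p1) + p2(1 − p2)]:

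- n per arm = (1.960·A + 0.8416·B)² / 0.05²
- power = Φ[(0.05·√n − 1.960·A) / B]

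**1. The plan's own figure: 93% v 98%.** p̄ = 0.955, A = √0.08595 = 0.2932, B = √0.0847 = 0.2910.

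- n = (0.5746 + 0.2449)² / 0.0025 = 268.7, so 269 per arm and 538 in total. This is the synopsis figure exactly.
- Power at 272 = Φ[(0.8246 − 0.5746)/0.2910] = Φ(0.859) = 80.5%.

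**2. 93% as the mean of the arms: 90.5% v 95.5%.** p̄ = 0.93, A = √0.1302 = 0.3608, B = √0.12895 = 0.3591.

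- n = (0.7072 + 0.3022)² / 0.0025 = 407.6, so 408 per arm and 816 in total.
- Power at 272 = Φ[(0.8246 − 0.7072)/0.3591] = Φ(0.327) = 62.8%.
- The difference detectable with 80% power at 272 per arm and a mean of 93% is 6.1 points.

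**3. All placements together.**

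| Arms | n per arm for 80% | Power at 269 | Power at 272 | Power at 280 (all 560) |
|---|---|---|---|---|
| 93 v 98 | 269 | 80.0% | 80.5% | 81.6% |
| 90.5 v 95.5 | 408 | 62.3% | 62.8% | 64.1% |
| 88 v 93 (sensitivity only) | 539 | 50.7% | 51.1% | 52.3% |

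Taking the ends of the Abstract's 90–95% range as the two arms gives 435 per arm, and 60.1% power at 272.

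**4. Does the result depend on the test assumed?** At 272 per arm:

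| Method | 93 v 98 | 90.5 v 95.5 |
|---|---|---|
| Pooled z, two-sided 0.05 | 80.5% | 62.8% |
| Unpooled (95% CI for the risk difference excludes 0) | 80.9% | 63.2% |
| Exact enumeration of the pooled z-test | 83.0% | 64.0% |
| One-sided 0.05 | 88.0% | 74.0% |

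The mean-of-arms reading falls short of 80% in every row. The one-sided version does not reproduce the plan's 80% for 93 v 98.

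**5. The null as worded.** To reject a difference of at most 5 points, power is approximately Φ[(δ − 0.05)/SE − z]. At δ = 0.05 the first term is zero for any n, so power = Φ(−z): 2.5% if the 95% CI must lie wholly beyond 5 points (z = 1.960), or 5% with a one-sided 0.05 test (z = 1.645). At 272 per arm and a mean of 93%, 80% power against this null needs a true difference of 11.0 points (z = 1.960) or 10.3 points (z = 1.645).

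**6. Is 98% supported as a first-shock rate?** The Abstract puts cardioversion success at 90–95%. The high rates in section 1.4 (97.9% and 100%; 97% in both groups; 93% v 97% at maximum energy) come from escalating multi-shock protocols, so they are cumulative rates. The fourth comparison there found 95% with RBW and 90.9% with BTE, though without 360J BTE shocks. None of these is a first-shock rate at full output.

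**The case against.** The sample size was not miscalculated. An exact match to 269 is good evidence that 93% was entered as the lower arm against 98%, and in section 12.2 the word mean follows a literature summary, so it may denote a reference rate rather than the average of the arms. A sample size built on a clinically meaningful difference need not claim that the alternative rate is expected. The closest cited comparison, 93% v 97% at maximum energy, has 93% as the lower arm, and the protocol cites evidence that fixed maximum energy outperforms escalation. The fourth study used a different BTE device and did not reach 360J, so it says little about this trial. No test against a 5-point margin is planned, so the null may simply be a badly worded target difference. Finally, 538 v 544 moves power by only half a point, and the planned 95% CI will show the precision achieved.

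Much of this stands. The arithmetic is sound for 93% v 98%, and the 63% figure is conditional on how 93% is read. But the 98% remains unstated and unsupported as a first-shock rate. Both the mean in section 12.2 and the synopsis's reference to the trial's own population can fairly be read as the overall rate. The wording of the null appears in two places and agrees with the hypothesis in section 5.1.1, so it is not an isolated slip. The 95% CI guards against over-reading a null result but does not correct the stated power.

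**Conclusion.** The concern holds. The stated 80% is right for 93% v 98% tested against zero difference and for no other reading that the documents support. On the mean-of-arms reading it is 62.8% at 272 per arm. Against the null as written it is about 2.5% to 5% for a true 5-point difference, whatever the sample size. The first two figures assume a two-sided 0.05 test; a one-sided 0.05 test raises the mean-of-arms figure to 74.0%, still short of 80%. The problem with the null does not depend on how 93% is read. The discrepancy between 538 and 544 is real but minor. This should be corrected before the power claim is relied on; it does not undermine the planned analysis.

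**What to change.** In section 12.2 and the synopsis:

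- State both arm rates, alpha, sidedness and test.
- Replace the null of a difference below 5% with the zero-difference null that the calculation uses, keep 5 points as the difference to be detected, and align section 5.1.1.
- Give power at 272 per arm as 80% for 93% v 98% only, and about 63% if the arms average 93% (detectable difference about 6.1 points), with about 51% for 88% v 93% as a sensitivity figure.
- Justify 98% as a first-shock rate at full output, or qualify the claim of adequate power for 5 points in sections 1, 1.3 and 1.4.
- Use one evaluable number throughout; sections 12.2 and 8.1.2 already use 544.

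The cost is a few sentences. No patients are added and no procedure changes. The only drawback is a less favourable stated power.

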5. INVESTIGATIONAL PLAN

5.1 General Schema of Study Design

5.1.1 Hypothesis

We hypothesize that the maximal output first shock efficacy of RBW and BTE shocks differs by more than 5%.

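### The 80% power is claimed against a null of a difference below 5 points, but 5 points, the only effect size given, is the edge of that null

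*Combined protocol and SAP*

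**What the plan says.** The power statement appears twice, with the same null and different sizes.

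- Protocol Synopsis, Statistical and Analytical Plan: 538 subjects, 269 per group, to "provide 80% power to reject the null hypothesis (a difference of efficacy < 5" percent. The rate assumption is "we expect the first shock DCCV success rate to be 93% in our population".
- Section 12.2: 544 patients, 272 per group, "needed to provide a power of 80% to reject the null hypothesis (a difference in efficacy of < 5" percent. The rate assumption is "We therefore estimate that the mean first shock success rate will be 93" percent.

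Section 5.1.1 gives the matching alternative: "We hypothesize that the maximal output first shock efficacy of RBW and BTE shocks differs by more than 5" percent.

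Two other places treat 5 points as the difference the trial should be able to find. Section 12.2 says "A clinically meaningful difference in first full output shock efficacy is 5" percent. Section 1.4 criticises an earlier randomised study because "a clinically relevant efficacy difference of 5% or more was impossible to detect".

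No section gives a true difference larger than 5 points as a planning assumption, separate success rates for the two arms, or the alpha for this calculation.

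**The concern.** Power is the chance of rejecting the null when a stated alternative is true, and that alternative must lie outside the null. Here the null covers all differences below 5 points and the only difference offered as an alternative is 5 points. A trial sized on that difference sits on the edge of the null, where the chance of rejection is fixed at the type I error and more patients do not raise it.

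This is the only sizing statement for the first primary endpoint. Taken literally, it invites a reader to treat a significant result as evidence of a difference above 5 points, which the trial was not sized to show. Taken as loose wording for a test of zero difference, it invites a reader to treat a non-significant result as having had 80% power against 5 points. That holds only for one pair of arm rates, which the plan does not state.

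**Working it through.** **Inputs.** Success rate 93% and difference 5 points (12.2); power 80% (synopsis and 12.2); 1:1 allocation (5.3); 269 per group (synopsis) and 272 per group (12.2). Alpha is not stated. I assume two-sided 0.05, in line with the 95% confidence intervals planned in the synopsis, so z = 1.960 for alpha and 0.842 for power.

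**1. Reproducing the plan's own figure.** For a test of zero difference with pooled variance:

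n per arm = [1.960·√(2·p̄·(1−p̄)) + 0.842·√(p1(1−p1) + p2(1−p2))]² / (p1−p2)²

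For 93% versus 98%, p̄ = 0.955:

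- 1.960·√0.08595 = 0.5746
- 0.842·√(0.0651 + 0.0196) = 0.2449
- n = (0.8195)² / 0.0025 ≈ 268.7, so 269 per arm and 538 in total

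This is the synopsis figure exactly. Non-inferiority with a 5-point margin (409 per arm at one-sided 0.025, 322 at 0.05) and equivalence (548 and 447) give neither 269 nor 272.

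**2. The null as written.** Rejecting a null of a difference up to 5 points, in the tested direction, has probability Φ((d − 0.05)/SE − 1.960).

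- At d = 0.05 the first term is zero for any sample size, so the probability is Φ(−1.960) = 2.5% (5% if alpha were one-sided 0.05).
- Exact check: the chance that the 95% CI lies wholly beyond 5 points when the true difference is 5 points is 1.9%, 2.2% and 2.4% at 272 per arm for 93% v 98%, 95.5% v 90.5% and 93% v 88%. At 2,000 per arm it is 2.2%, 2.4% and 2.4%.
- For 80% power at 272 per arm, d must equal 0.05 + 2.802·SE. That is about 11.0 points centred on 93%, 11.3 points with an upper rate of 98%, and 13.1 points with an upper rate of 93%.
- If 93% is the lower rate, the reading that reproduces 269, the difference cannot exceed 7 points. At 93% versus 100%, SE = √(0.0651/272) = 0.0155, so 0.05 + 2.802 × 0.0155 = 0.093. The required 9.3 points is out of reach.

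**3. A null of zero, 5 points as the difference to detect.** Power = Φ([0.05·√n − 1.960·√(2p̄(1−p̄))] / √(p1(1−p1) + p2(1−p2))). At n = 272, 0.05·√272 = 0.8246:

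- 93% v 98%: (0.8246 − 0.5746)/0.2910 = 0.859
- 95.5% v 90.5%: (0.8246 − 0.7072)/0.3591 = 0.327
- 93% v 88%: (0.8246 − 0.8127)/0.4132 = 0.029

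| Arm rates | Role of 93% | n per arm for 80% | Power at 269 | Power at 272 | Exact power at 272 | Detectable difference, 80% power, 272 per arm |
|---|---|---|---|---|---|---|
| 93% v 98% | lower arm | 269 | 80.1% | 80.5% | 83.0% | 5.0 points |
| 95.5% v 90.5% | mean of both arms | 408 | 62.3% | 62.8% | 64.0% | 6.1 points |
| 93% v 88% | higher arm | 539 | 50.7% | 51.2% | 51.5% | 7.4 points |

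On the middle row a true 5-point difference is missed 100 − 62.8 = 37.2% of the time, against the 20% implied by the plan.

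**The case against.** The strongest reply is that this is a slip of wording with no effect on the trial. The planned analysis is a risk difference and risk ratio with 95% confidence intervals, and no section makes a decision by testing the 5-point null. The synopsis size is reproduced exactly by a sensible calculation. On that view the intent is clear and the size is right. Much of this stands: data collection, estimates and intervals are unaffected, and enrolment can stay as it is if 93% versus 98% was meant.

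A second reply is that calling 93% a mean need not refer to the average of the two arms. The phrase follows a summary of earlier studies and may only mean an average expected from the literature; the synopsis omits the word. This is fair, and the 63% and 51% figures are sensitivities, not what the sponsor is known to have assumed. But the plan does not settle it. A 98% first-shock rate lies above both ranges cited in 12.2 (first shock 54% to 90%, at less than maximum energy; overall 90% to 97%), although 1.4 reports overall success of 97.9% and 100% after escalating shocks in one study. A rate on which the 80% depends should be stated and justified.

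A third reply is that power against the written null does reach 80% at true differences of about 11 to 13 points. That is correct, and the accurate claim is that 80% does not hold at 5 points. No section assumes a difference of that size.

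Two limits remain. Only 269 is reproduced exactly; 272 is compatible but unexplained, and the 538/544 disagreement is a separate matter. The powers above also take a single test at full alpha, without allowance for the analysis at 50% enrolment or the three primary endpoints.

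**Conclusion.** The concern holds. At the only difference the plan names, the chance of rejecting the null as written is about 2.5%, not 80%, and no increase in sample size changes that. This depends on neither the arm rates nor the inferred 98%; another alpha would change only the small rejection rate.

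That 5 points was meant as the difference to detect from zero is an inference, but well supported by 12.2, by 1.4 and by the exact match to 269. On that reading the 80% holds for 93% versus 98%. It falls to about 63% if 93% is the mean of both arms and about 51% if 93% is the higher arm, assuming two-sided alpha 0.05 and 272 per arm. The power statement should be corrected; the sample size may stand, subject to the sponsor confirming the rates.

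**What to change.** In the synopsis and section 12.2, replace the power statement with text such as:

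> H0: risk difference = 0; H1: risk difference not equal to 0; two-sided alpha [sponsor to confirm; 0.05 assumed here]. The difference to detect is 5 percentage points, [rate]% versus [rate]% [sponsor to confirm both].

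Then give the power that belongs to the confirmed rates, taken from the table above or recomputed if alpha differs or is shared with the interim analysis or the other primary endpoints. Say in 12.2 whether 93% is one arm's rate or the mean of the two, and justify the other rate. Bring 5.1.1 into line with the restated null. If a claim of more than 5 points is to be kept, make it only when the 95% CI for the risk difference lies wholly beyond 5 points, and attach no 80% power to it.

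The cost is wording in three places. Data collection and the planned analysis do not change. If the confirmed rates are not 93% versus 98%, the sponsor either states the lower power or plans about 408 per arm (95.5% v 90.5%) or 539 per arm (93% v 88%). The trial also gives up any claim of being powered to show a difference above 5 points.
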